Eye disorders- any other	CTCAE Grade 3 for > 14 consecutive days
	CTCAE Grade 4
Gastrointestinal disorders	Diarrhea CTCAE Grade $\geq 3 \geq 48$ hrs, despite the use of optimal anti-diarrhea therapy
	Nausea or vomiting CTCAE Grade $\geq 3 \geq 48$ hrs, despite the use of optimal anti-emetic therapy
	Pancreatitis CTCAE Grade ≥ 3
Investigations (Renal)	Serum creatinine CTCAE Grade ≥ 3
Investigations (Hepatic) ^c	Blood bilirubin (total bilirubin) CTCAE Grade ≥ 3
	AST or ALT CTCAE Grade ≥ 3 in conjunction with blood (total) bilirubin CTCAE Grade ≥ 2 of any duration
	AST or ALT CTCAE Grade 3 for > 7 consecutive days
	AST or ALT CTCAE Grade 4.
	Serum alkaline phosphatase CTCAE Grade 4 > 7 consecutive days

Toxicity	Any of the following criteria:
Investigations (Metabolic)	Serum lipase and/or serum amylase (asymptomatic) CTCAE Grade 3 > 7 consecutive days
	Serum lipase and/or serum amylase (asymptomatic) CTCAE Grade 4
Cardiac disorders	≥ CTCAE Grade 3
Investigations (Cardiac)	Serum CK/CPK CTCAE Grade 3 for > 14 consecutive days if clinically significant (symptomatic)
	Serum CK/CPK CTCAE Grade 4 for > 14 consecutive days
	QTcF interval ≥ 501 ms on at least two separate ECGs (only for triple combination)
Vascular disorders	Persistent hypertension CTCAE Grade ≥ 3 requiring more than one drug or more intensive therapy than previously
General disorders and administration site conditions	Fatigue CTCAE Grade 3 for > 7 consecutive days
	Edema CTCAE grade 3 for > 14 consecutive days
Other Adverse Events ^d	Any other CTCAE Grade ≥ 3 toxicity (except SCC ^e)

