6.3 Dose modifications

6.3.1 Dose modification and dose delay

Patients will be monitored for adverse events at each visit with the NCI CTCAE version 4.03 used for all grading. If a patient develops toxicity, the dose may be adjusted as outlined in [Table 6-4](#), which includes criteria for interruption and re-initiation of LGX818 and/or MEK162 and/or LEE011, as applicable. All dose modifications should be based on the worst preceding toxicity (CTCAE version 4.03).

All dosing interruptions and changes must be recorded on the Dosage Administration Record eCRF.

If a patient experiences a DLT, study treatment should be interrupted and the toxicity should be followed as described in [Section 6.2.6](#).

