6.3.2 Treatment interruption and treatment discontinuation

Each patient is only allowed a maximum of two dose reductions after which the patient will be discontinued from the study treatment. In addition, a patient should discontinue treatment with the LGX818 and MEK162 dual or LGX818 and MEK162 and LEE011 triple combination if, after treatment is resumed at a lower dose, the toxicity recurs with the same or worse severity. However, the patient may continue to receive study treatment at the next lower dose level, if appropriate, at the discretion of the Investigator and in discussion with the Sponsor. If, after interruption of treatment and resolution, treatment is resumed at the same dose following the criteria in [Table 6-4](#) and the same toxicity recurs with the same or worse severity, next treatment re-initiation must resume at the next lower dose level irrespective of duration. For each patient,

once a dose level reduction has occurred, the dose level may not be re-escalated during subsequent treatment cycles, except in cases where LGX818 dosing was reduced to 450mg QD during MEK162 dosing interruption.

Dose reduction for LGX818 and/or MEK162 and/or LEE011, as applicable means treatment at the next lower dose level of the respective study drug. For LGX818 and LEE011, this is the next lower previously tested dose level. For MEK162 this is the next lower dose level (please see [Table 6-1](#) and [Table 6-2](#)). If a patient requires a dose interruption of >21 days from the intended day of the next scheduled dose, then the patient must be discontinued from the study treatment unless the patient has experienced objective evidence of clinical benefit. If the patient has experienced objective evidence of clinical benefit, and in the opinion of the investigator it is in the best interest of the patient to remain on study, then following discussion with the sponsor, the patient may continue on study treatment.

Table 6-4 Criteria for interruption and re-initiation of LGX818/MEK162/LEE011 triple-combination treatment

Recommended Dose Modifications for (dual) LGX818 and MEK162 or (triple) LGX818 and MEK162 and LEE011 combination study treatment	
Worst Toxicity CTCAE v4.03 Grade (unless otherwise specified)^a	Recommended Dose Modifications any time during a cycle of therapy
No toxicity	Maintain dose level
Blood and lymphatic system disorders	
Anemia (Hemoglobin)	

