Grade 3 (PLT < 50 – 25 x 10 ⁹ /L)	Interrupt dosing of LGX818 and MEK162 (and LEE011 in patients treated in triple-combination arm) until resolved to ≤ Grade 1, then: - If resolved in ≤ 7 days, then maintain dose level of LGX818 and MEK162 (and LEE011 in patients treated in triple-combination arm). - If resolved in > 7 days and/or with signs of bleeding, then ↓ 1 dose level* of LGX818 and MEK162 (and LEE011 in patients treated in triple-combination arm)
Grade 4 (PLT < 25 x 10 ⁹ /L)	Discontinue patient from study drug treatment.

Recommended Dose Modifications for (dual) LGX818 and MEK162 or (triple) LGX818 and MEK162 and LEE011 combination study treatment	
Worst Toxicity CTCAE v4.03 Grade (unless otherwise specified)^a	Recommended Dose Modifications any time during a cycle of therapy
Gastrointestinal disorders	
Diarrhea	
Grade 1	Maintain dose level of LGX818 and MEK162 (and LEE011 in patients treated in triple-combination arm), but initiate anti-diarrhea treatment.
Grade 2	Interrupt dosing of LGX818 and MEK162 (and LEE011 in patients treated in triple-combination arm) until resolved to Grade ≤ 1 with proper therapy and monitoring and then maintain dose level of LGX818 and MEK162 (and LEE011 in patients treated in triple-combination arm) - For 2 nd occurrence of diarrhea Grade 2 within 15 days, interrupt dosing of LGX818 and MEK162 (and LEE011 if applicable) until resolved to Grade ≤ 1, then reduce MEK162 and LGX818 (and LEE011 in patients treated in triple-combination arm) by 1 dose level* and maintain dose level of LGX818 (and LEE011 in patients treated in triple-combination arm)
Grade 3	Interrupt dosing of LGX818 and MEK162 (and LEE011 in patients treated in triple-combination arm) until resolved to Grade ≤ 1, then reduce dose of LGX818 and MEK162 (and LEE011 in patients treated in triple-combination arm) by 1 dose level*.
Grade 4	Discontinue patient from study drug treatment.
Note: Anti-diarrhea medication is recommended at the first sign of abdominal cramping, loose stools or overt diarrhea.	
Nausea / Vomiting	
Grade 1	Maintain dose level of LGX818 and MEK162 (and LEE011 in patients treated in triple-combination arm)

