Grade 2 (> 1.5 – 2.0 x ULN)	Interrupt dosing until recovery to G1 with proper therapy and monitoring – Re-initiate MEK162 and LGX818 (and LEE011 in patients treated in triple-combination arm) at same dose level – If recurs at G2, interrupt dosing of MEK162 and LGX818 (and LEE011 in patients treated in triple-combination arm) until recovery to G1 and then re-initiation at next lower dose level.
Grade 3 (> 2.0 – 5.0 x ULN)	Interrupt dosing of LGX818 and MEK162 (and LEE011 in patients treated in triple-combination arm) until resolved to Grade ≤ 2, then: - If resolved in ≤ 7 days, maintain dose level of LGX818 and MEK162 (and LEE011 in patients treated in triple-combination arm) - If resolved in > 7 days, ↓ 1 dose level* of LGX818 and MEK162 (and LEE011 in patients treated in triple-combination arm).
Grade 4 (> 5.0 x ULN)	Discontinue patient from study drug treatment.

Note: A CT scan or other imaging study to assess the pancreas, liver, and gallbladder must be performed within 1 week of the first occurrence of any grade ≥ 3 of amylase and/or lipase. In cases of asymptomatic elevations of lipase and/or amylase with imaging study which does not show damage to pancreas, liver, and gallbladder, if the patient is asymptomatic Grade 2 elevations of lipase and/or amylase occur again at the reduced dose, patients will be discontinued permanently from study treatment.

Recommended Dose Modifications for (dual) LGX818 and MEK162 or (triple) LGX818 and MEK162 and LEE011 combination study treatment	
Worst Toxicity CTCAE v4.03 Grade (unless otherwise specified)^a	Recommended Dose Modifications any time during a cycle of therapy
Cardiac disorders	
Cardiac general	
Grades 1 or 2	Maintain dose level of LGX818 and MEK162 (and LEE011 in patients treated in triple-combination arm)
Grade 3	Interrupt dosing of LGX818 and MEK162 (and LEE011 in patients treated in triple-combination arm) until resolved to Grade ≤ 1, then ↓ 1 dose level* of LGX818 and MEK162 (and LEE011 for triple-combination arm)
Grade 4	Discontinue patient from study drug treatment.
Investigations (cardiac)	
Creatine phosphokinase (CPK)	
Grade 1 (> ULN – 2.5 x ULN) or Grade 2 (> 2.5 – 5.0 x ULN)	Maintain dose level of LGX818 and MEK162 (and LEE011 in patients treated in triple-combination arm)

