Grade 2	Interrupt dosing of MEK162 (and LEE011 in patients treated in triple-combination arm) for ≤ 21 days. -If resolved to Grade ≤ 1 in ≤ 21 days, reduce 1 dose level ^h of MEK162 (and LEE011 in patients treated in triple-combination arm), performing an individualized benefit-risk assessment -If not resolved to Grade ≤ 1 in ≤ 21 days, then discontinue patient from study drug treatment. If Grade 2 recurs, discontinue patient from study drug treatment
Grade 3/4	Discontinue patient from study drug treatment
General disorders and administration site conditions	
Fatigue	
Grades 1 or 2	Maintain dose level of LGX818 and MEK162 (and LEE011 in patients treated in triple-combination arm)
Grade 3	Interrupt dosing of LGX818 and MEK162 (and LEE011 in patients treated in triple-combination arm) until resolved to Grade ≤ 1, then: - If resolved in ≤ 7 days, maintain dose level of LGX818 and MEK162 (and LEE011 in triple-combination arm) - If not resolved after > 7 days, then ↓ 1 dose level* of LGX818 and MEK162 (and LEE011 in patients treated in triple-combination arm)
Edema	
Grades 1 or 2	Maintain dose level of LGX818 and MEK162 (and LEE011 in patients treated in triple-combination arm)

Recommended Dose Modifications for (dual) LGX818 and MEK162 or (triple) LGX818 and MEK162 and LEE011 combination study treatment	
Worst Toxicity CTCAE v4.03 Grade (unless otherwise specified)^a	Recommended Dose Modifications any time during a cycle of therapy
Grade 3	Interrupt dosing of LGX818 and MEK162 (and LEE011 in patients treated in triple-combination arm) until resolved to Grade ≤ 1, then: - If resolved in ≤ 14 days, then ↓ 1 dose level* of MEK162 and maintain dose of LGX818 (and LEE011 in patients treated in triple-combination arm) - If not resolved after > 14 days, then discontinue patient from study drug treatment.
Other adverse events	
Grades 1 or 2	Maintain dose level of LGX818 and MEK162 (and LEE011 in patients treated in triple-combination arm)
Grade 3	Interrupt dosing of LGX818 and MEK162 (and LEE011 in patients treated in triple-combination arm) until resolved to Grade ≤ 1, then ↓ 1 dose level* of LGX818 and MEK162 (and LEE011 in triple-combination arm)
Grade 4	Discontinue patient from study drug treatment.

^a All dose modifications should be based on the worst preceding toxicity.

^b Not CTCAE grading

^c Dose reduction below 50 mg QD for LGX818, and below 15 mg BID for MEK162 is not allowed.

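### Table 6-4, asymptomatic amylase/lipase: after a Grade 3 peak dosing may resume at Grade 2 (up to 2.0 x ULN), a level at which a milder Grade 2 event must stay on hold until Grade 1 (up to 1.5 x ULN)

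*Protocol*

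**What the plan says.** The block for asymptomatic amylase and/or lipase elevation in Table 6-4 (Protocol Section 6.3.2) sets these rules:

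- **Grade 1**, above ULN to 1.5 x ULN: dose maintained.
- **Grade 2**, above 1.5 to 2.0 x ULN: "Interrupt dosing until recovery to G1 with proper therapy and monitoring", then restart at the same dose. If Grade 2 recurs, hold again to Grade 1 and restart one level lower.
- **Grade 3**, above 2.0 to 5.0 x ULN: "Interrupt dosing of LGX818 and MEK162 (and LEE011 in patients treated in triple-combination arm) until resolved to Grade ≤ 2, then" restart at the same dose if this took no more than 7 days, or one level lower if longer.
- **Grade 4**, above 5.0 x ULN: discontinue.

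A note under the block requires imaging within 1 week of the first Grade 3 or higher value. It also says that if "Grade 2 elevations of lipase and/or amylase occur again at the reduced dose, patients will be discontinued permanently from study treatment".

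Footnote a of the table fixes which row applies: "All dose modifications should be based on the worst preceding toxicity". Section 6.3.1 says the same.

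**The concern.** Release levels in a dose-modification table should be at least as strict after a severe event as after a mild one. Here the order is reversed. A patient recovering from a Grade 3 enzyme rise may resume all study drugs at a value that the row above treats as a reason to withhold them.

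What is at stake is dosing safety and consistent conduct across sites. The rule still operates: patients remained on treatment at Amendment 10, Table 7-2 keeps clinical chemistry on the schedule, and Section 7.2.2.5.2 includes amylase and lipase in that panel.

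**Working it through.** The plan gives no figure to reproduce, so the check sets the rows side by side using the limits printed in Table 6-4.

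**Release ceilings**

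- After a Grade 2 peak: top of Grade 1 = 1.5 x ULN.
- After a Grade 3 peak: top of Grade 2 = 2.0 x ULN.
- Difference: 2.0 − 1.5 = 0.5 x ULN. Ratio: 2.0 / 1.5 = 1.33.
- Band in which the rows disagree: above 1.5 to 2.0 x ULN.

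**Example, both patients now at 1.8 x ULN**

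- Patient A peaked at 1.9 x ULN (Grade 2). The value is above 1.5, so the hold continues.
- Patient B peaked at 4.0 x ULN (Grade 3). The value is not above 2.0, so dosing may resume, at the full previous dose if within 7 days.

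**Does another rule reconcile the rows?**

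- Under the worst-preceding-toxicity rule, the Grade 3 row governs patient B.
- If a site instead re-applies the Grade 2 row at restart, patient B is released by one row and interrupted by the other on the same value. The rows then conflict directly.
- The imaging note sets no release level.
- The recurrence rule in Section 6.3.2 sets the dose after a recurrence, not the enzyme level at which dosing may resume.

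**Other toxicities that pair a Grade 2 hold with a Grade 3 restart**

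| Toxicity | Release after Grade 2 | Release after Grade 3 |
|---|---|---|
| Thrombocytopenia | Grade ≤ 1 | Grade ≤ 1 |
| Diarrhea | Grade ≤ 1 | Grade ≤ 1 |
| Nausea/vomiting | Grade 1 | Grade ≤ 1 |
| Bilirubin | Grade ≤ 1 | Grade ≤ 1 |
| QTcF | < 481 ms | < 481 ms |
| Hypertension | Grade 1 | Grade ≤ 1 |
| AST/ALT | Grade ≤ 1 (≤ 2 with liver metastasis) | baseline grade or better |
| **Amylase/lipase** | **Grade 1** | **Grade ≤ 2** |

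Six of the seven comparison rows use one level after both holds. The thrombocytopenia Grade 3 cell, for instance, reads "until resolved to ≤ Grade 1, then". AST/ALT follows a different rule. The comparison concerns release after a hold only: notes under nausea/vomiting and bilirubin let some Grade 3 events continue without one. Neutropenia and anemia release Grade 3 at Grade 2 or better, but neither holds at Grade 2, so neither is inverted.

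**The case against.** The strongest counter-argument is that the Grade 2 row, not the Grade 3 row, may be the one out of step. The Grade 3 row mirrors the dose-limiting-toxicity criterion in Table 6-3, "Serum lipase and/or serum amylase (asymptomatic) CTCAE Grade 3 > 7 consecutive days": hold to Grade 2 or better, with a 7-day cut for dose reduction. Neutropenia has the same structure and needs no hold at Grade 2. The Grade 2 amylase/lipase wording recurs in several other blocks (nausea/vomiting, pancreatitis, creatinine, hypertension) and may have been carried over as stock text. This stands as a reason not to treat the direction of the fix as settled. It does not remove the inversion.

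The limits on impact also stand. The table gives recommendations, the finding is asymptomatic, imaging is mandatory after Grade 3, and a recurrence at the same dose forces a reduction.

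Three stronger readings are tempting but not supported:

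- **That every other row keeps one release level.** AST/ALT does not, so the count is six of seven.
- **That the note forces permanent discontinuation of a patient who restarts one level lower while still at Grade 2.** The note concerns elevations that happen again, which ordinarily means a recurrence, not a value carried over from the hold.
- **That the AST/ALT Grade 2 rule with liver metastasis is the same defect.** Its release level is already met at onset, but Table 6-3 footnote c makes a similar liver-tumor allowance and exclusion criterion 7 admits such patients up to 5 x ULN. It looks deliberate, is not an inversion, and needs at most a separate wording clarification.

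**Conclusion.** The inversion is printed and nothing elsewhere in the protocol resolves it. Followed exactly, the table lets the more severe asymptomatic amylase/lipase event restart at up to 2.0 x ULN while the milder one waits for 1.5 x ULN, a gap of 0.5 x ULN. This rests only on the printed grade limits and on the worst-preceding-toxicity rule. The alternative reading, re-applying the Grade 2 row at restart, gives a direct conflict instead of coherence.

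The impact is minor. Ten patients were on treatment as of Amendment 10, and enrolment is closed (Section 14.10.1). A reader might infer that patients were harmed or that an efficacy or dose-finding result is in doubt. The document gives no evidence of harm, and no inferential result depends on this cell.

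**What to change.** Align the two rows. The cautious option is to rewrite the Grade 3 cell with two separate conditions: restart only at Grade 1 or better, and keep the dose if Grade 2 or better was reached within 7 days, otherwise go one level lower. Both rows then release at 1.5 x ULN or below, and the dose-reduction cut still matches the Table 6-3 definition.

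The cost is a somewhat longer hold after Grade 3, which counts toward the limit in Section 6.3.2 ("If a patient requires a dose interruption of >21 days from the intended day of the next scheduled dose"). The change also needs a written amendment with the approvals in Section 12.1. Amendment 10 already revised Table 6-4, so this is an ordinary kind of change.

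If the sponsor judges Grade 2 values safe for dosing, the Grade 2 hold should be relaxed instead. The note's discontinuation trigger at Grade 2 would then need revisiting too.

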Grade 3 (> 5.0 – 10.0 x ULN)	If asymptomatic: Maintain dose level of LGX818 and MEK162 (and LEE011 in triple-combination arm) If symptomatic: Interrupt dosing of MEK162 and maintain dose of LGX818 ¹ (and LEE011 in patients treated in triple-combination arm) until resolved to Grade ≤ 1, then: - If resolved in ≤ 14 days, then ↓ 1 dose level* of MEK 162 and maintain dose level of LGX818 ² (and LEE011 in patients treated in triple-combination arm) - If unresolved after > 14 days, then discontinue patient from study drug treatment.
Grade 4 (> 10.0 x ULN)	Interrupt dosing of MEK162 and maintain dose of LGX818 ¹ (and LEE011 in triple-combination arm) until resolved to CTCAE Grade ≤ 1, then: - If resolved in ≤ 14 days, then ↓ 1 dose level of MEK162 and maintain dose level of LGX818 ² (and LEE011 in patients treated in triple-combination arm) - If unresolved after > 14 days, then discontinue patient from study drug treatment.
¹ If the LGX818 dose is > 450mg QD, then the LGX818 dose must be reduced to 450mg QD during the MEK162 dosing interruption. ² If the LGX818 dose was reduced to 450mg QD during an MEK162 interruption, it must be re-escalated to the previous dose once MEK162 dosing resumes.	

Recommended Dose Modifications for (dual) LGX818 and MEK162 or (triple) LGX818 and MEK162 and LEE011 combination study treatment

Worst Toxicity CTCAE v4.03 Grade (unless otherwise specified)^a

Recommended Dose Modifications any time during a cycle of therapy

Left ventricle (LV) systolic dysfunction (not according to CTCAE)

Asymptomatic decrease of > 10% in left ventricle ejection fraction (LVEF) compared to baseline and the ejection fraction is below the institution's lower limit of normal and CTCAE Grade 2

Interrupt dosing of MEK162 until LVEF recovers (defined as \geq LLN and decrease \leq 10% compared to baseline).
- If the LVEF recovers \leq 21 days, then \downarrow 1 dose level of MEK162, maintain dose of LGX818 and LEE011 in patients treated in triple-combination arm, monitor LVEF 2 weeks after restarting on MEK162, every 4 weeks for 12 weeks and subsequently as per protocol
- If the LVEF recovers > 21 days, then discontinue patient from study drug treatment and closely monitor LVEF until resolution (or for 16 weeks).

Grade \geq 3

Discontinue patient from study drug treatment.

Electrocardiogram QTcF interval prolonged

Grade 1 (QTcF 450-480 ms)^f

Maintain dose level(s). Perform steps 1-4 as directed in "For all grades."

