Grade 3	Interrupt dosing of LGX818 and MEK162 (and maintain dose level of LEE011 in patients treated in triple-combination arm) and refer patient to ophthalmologist monitoring within one week. ^g - If resolved to Grade ≤ 1 in ≤ 21 days, reduce 1 dose level ^h of LGX818 and MEK162 - If not resolved to Grade ≤ 1 in > 21 days, discontinue patient from study drug treatment and refer the patient to an ophthalmologist for monitoring. ^h
Grade 4	Discontinue patient from study drug treatment and refer the patient to an ophthalmologist for monitoring. ^g
Skin and subcutaneous tissue disorders	
Rash / hand foot skin reaction (HFSR) / photosensitivity / Toxic Epidermal Necrolysis (TEN)	
Grade 1	Maintain dose level of LGX818 and MEK162 (and LEE011 in patients treated in triple-combination arm), but consider initiating appropriate skin toxicity therapy (See Appendix 3).
Grade 2	Maintain dose level of LGX818 and MEK162 (and LEE011 in patients treated in triple-combination arm), but initiate/intensify appropriate skin toxicity therapy.
Grade 3 despite skin toxicity therapy	Interrupt dosing of LGX818 and MEK162 (and LEE011 in patients treated in triple-combination arm), until resolved to Grade ≤ 1 then: - If resolved in ≤ 7 days, ↓ 1 dose level* of LGX818 and MEK162 (and LEE011 in triple-combination arm) - If not resolved after > 7 days, discontinue patient from study drug treatment.
Grade 4 despite skin toxicity therapy	Discontinue patient from study drug treatment.

Recommended Dose Modifications for (dual) LGX818 and MEK162 or (triple) LGX818 and MEK162 and LEE011 combination study treatment	
Worst Toxicity CTCAE v4.03 Grade (unless otherwise specified)^a	Recommended Dose Modifications any time during a cycle of therapy
Respiratory, thoracic and mediastinal disorders	
ILD/Pneumonitis	Maintain dose level of LGX818; adjust dose of MEK162 (and LEE011 in patients treated in triple-combination arm) according to Grade below
Grade 1	No dose interruption or adjustment of MEK162 (or LEE011 in patients treated in triple-combination arm) is required. Initiate appropriate medical therapy and monitor as clinically indicated

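### Table 6-4 continues LGX818 unchanged while MEK162 is held for Grade 2 ILD/pneumonitis, without the 450 mg QD limit that the CPK rows make mandatory

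*Protocol*

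**What the plan says.** Three blocks of Table 6-4 hold MEK162 without holding LGX818.

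- **CPK, Grade 3 symptomatic and Grade 4.** The instruction is "Interrupt dosing of MEK162 and maintain dose of LGX818". Footnote 1 limits it: "If the LGX818 dose is > 450mg QD, then the LGX818 dose must be reduced to 450mg QD during the MEK162 dosing interruption". Footnote 2 adds that, if LGX818 was cut in this way, "it must be re-escalated to the previous dose once MEK162 dosing resumes".
- **ILD/pneumonitis.** The block opens with "Maintain dose level of LGX818; adjust dose of MEK162 (and LEE011 in patients treated in triple-combination arm) according to Grade below". At Grade 2 it continues: "Interrupt dosing of MEK162 (and LEE011 in patients treated in triple-combination arm) for ≤ 21 days". There is no 450 mg limit and no mark for footnote 1 or 2.
- **Left ventricular dysfunction (asymptomatic LVEF decrease).** The row says "Interrupt dosing of MEK162 until LVEF recovers". It does not say what happens to LGX818 during the hold.

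The body text of Section 6.3.2 mentions the reduction only as an exemption. Doses may not be re-escalated after a reduction, "except in cases where LGX818 dosing was reduced to 450mg QD during MEK162 dosing interruption".

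Section 6.2.2 gives 450 mg QD as the single-agent MTD of LGX818. It declares two RP2Ds for the dual combination: LGX818 450 mg QD and 600 mg QD, each with MEK162 45 mg BID.

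**The concern.** The CPK and ILD blocks create the same drug state, with MEK162 stopped and LGX818 continuing. Only the CPK block limits LGX818 in that state. Footnote 1 is triggered by the LGX818 dose and the MEK162 interruption, not by creatine kinase, and 450 mg is the single-agent MTD. The reason for the limit therefore applies whatever toxicity prompted the hold.

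The ILD block does more than leave out a detail: it positively tells the site to maintain LGX818. A site following it for a patient on 600 mg would give LGX818 without MEK162 above its single-agent MTD, to a patient with active Grade 2 pneumonitis.

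**Working it through.** This is mainly a comparison of text. The protocol gives no figure to reproduce beyond the doses themselves.

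**Step 1: the three blocks that hold MEK162 without holding LGX818**

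| Table 6-4 block | MEK162 | LGX818 during the hold | 450 mg limit |
|---|---|---|---|
| CPK Grade 3 symptomatic, Grade 4 | Held; discontinue if unresolved after 14 days | Maintained | Yes (footnotes 1 and 2) |
| LVEF decrease | Held; discontinue if recovery takes more than 21 days | Not stated | None |
| ILD/pneumonitis Grade 2 | Held up to 21 days | Maintained | None |

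One block in three carries the limit. The Grade 3 eye rows now hold LGX818 as well, so the question does not arise there.

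**Step 2: does any other text supply the limit?** Section 6.3.2 permits re-escalation after such a cut but does not order the cut. Footnote 1 names no toxicity, but it sits in the CPK block and is marked only there.

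**Step 3: does the amendment history show a deliberate exemption?** As background only, the Amendment 5 rationale lists CPK and the eye disorders when introducing the limit. The ILD rule came in Amendment 10, drawn from the MEK162 and LEE011 prescribing information. ILD could not have been on the earlier list, so its absence shows no decision to exempt it.

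**Step 4: size of the excess**

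- Dose at issue: 600 mg QD (RP2D, Section 6.2.2).
- Single-agent MTD: 450 mg QD (Section 6.2.2).
- Ratio: 600/450 = 1.33, or 33% above the MTD, for up to 21 days.

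**Step 5: what single-agent LGX818 did above 450 mg.** Section 1.2.1.2 lists five once-daily DLTs, at 100, 300, 550, 700 and 700 mg. Three of the five were above 450 mg. Patients per dose are not given, so this is not a rate. All were grade 3 and reversible.

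**Step 6: who could be affected.** The Amendment 10 rationale counts 5 dual + 5 triple = 10 patients on treatment, and Section 14.10.1 says enrollment is closed. The number above 450 mg is not stated. If the five triple patients are at Table 6-2 levels (all 450 mg LGX818 or less), the range is 0 to 5. The note to Table 6-2 allows 600 mg to be explored in the triple arm, which widens the range to 0 to 10.

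**The case against.** The case for treating this as a minor cross-reference gap has several parts.

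- **The wording may already cover it.** Footnote 1 is general, and Section 6.3.2 speaks of the reduction during MEK162 interruption without mentioning CPK. This does not settle the matter. The footnote marks appear only in the CPK rows, Section 6.3.2 orders nothing, and the ILD line says to maintain the dose. If the limit was meant for the whole table, the same small edit is still needed.
- **The table gives latitude.** It is headed as recommendations, and Section 6.3.1 says: "If a patient develops toxicity, the dose may be adjusted as outlined in" Table 6-4. This lets an investigator cut LGX818 but does not tell them to.
- **Follow-up is close.** Section 6.2.6 requires at least weekly follow-up for four weeks after an interruption for an adverse event, and other Table 6-4 rows hold LGX818 for several of its Grade 3 toxicities. This stands and limits the harm.
- **The toxicity evidence is thin.** Two of the three DLTs above 450 mg were at 700 mg, above the dose at issue, and there are no denominators. Section 6.2.2 calls adverse events up to 700 mg QD reversible and manageable. This stands.
- **Stopping LEE011 should not aggravate the problem.** Section 6.2.2 predicts that LEE011 200 mg raises the AUC of LGX818 450 mg by 29%, so stopping it should lower LGX818 exposure. This stands, and the concern rests on the absence of MEK162.
- **No affected patient is shown.** This stands too: the number may be zero, and no ILD incidence is given.
- **Footnote 2 would force a return to 600 mg after pneumonitis.** This fails. The CPK rows already pair a one-level MEK162 reduction with LGX818 re-escalation. The benefit-risk assessment in the ILD row concerns restarting MEK162 and LEE011.

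**Conclusion.** The concern holds. For one drug state, Table 6-4 imposes a mandatory LGX818 limit in the CPK rows and, in the ILD/pneumonitis block, tells sites to maintain LGX818 without that limit. For a patient at the 600 mg RP2D, the literal ILD rule gives 1.33 times the single-agent MTD without MEK162 for up to 21 days.

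This assumes that the site follows the ILD block as written and that at least one patient still takes more than 450 mg; the protocol does not establish the second point. Reversible toxicity, weekly follow-up and the small number of remaining patients keep the expected harm low. The point should be fixed because it bears on patient safety and costs almost nothing, but it is not a major defect.

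The LVEF row is a lesser matter. It is silent on LGX818 during the hold, so it needs clarification and is not a contradiction.

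**What to change.** 1. Mark CPK footnotes 1 and 2 on the ILD/pneumonitis Grade 2 row.
2. Reword the LGX818 line of the ILD block along these lines: *Maintain dose level of LGX818 (reduce to 450 mg QD if higher during MEK162 interruption).*
3. As a secondary clarification, state on the LVEF row whether the same limit applies while MEK162 is held.

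Section 6.3.2 already allows the later re-escalation and needs no change. The cost is two existing footnote marks, one reworded line and one clarifying phrase, with no new visit, procedure or data.
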